2.2 Analysis Sets

2.2.1 All Randomized (RAND) Analysis Set

The RAND analysis set consists of all participants who were randomized in the study. Analysis based on this analysis set will use the randomized treatment group assigned by IWRS (All randomized analysis set as Randomized).

2.2.2 Intent-to-Treat (ITT) Analysis Set

The ITT analysis set consists of all participants who were randomized and treated in the study. This analysis set will be used for the analysis of efficacy, subject information and virology assessments. Treatment group as randomized will be used for these analyses (ITT analysis set as Randomized).

2.2.3 Primary Analysis Set

The Primary analysis set consists of all participants in the ITT analysis set with confirmed critical COVID-19 disease defined as score of 4 or 5 on the CRS scale at baseline. For more details on CRS score please refer to Section 5: Efficacy. Treatment groups as randomized will be used for the analysis using this analysis set (Primary analysis set as Randomized).

2.2.4 All Subjects Treated (AST) Analysis Set

The AST analysis set consists of all participants who received the study drug. This analysis set will be used to evaluate the safety of drug, using the actual treatment received by a participant (AST analysis set as Treated)

2.2.5 Pharmacokinetics (PK) Analysis Set

The PK analysis set includes all participants in the AST analysis set with no interruption of study medication and who also had at least 1 valid blood sample drawn for PK analysis after dose of Sirukumab. This analysis set will be used to analyze the PK concentration using actual treatment received by a participant (PK analysis set as Treated).

2.2.6 Immunogenicity (IMG) Analysis set

The IMG analysis set consists of participants in AST analysis set who received a dose (full or partial) of Sirukumab during the study and have at least one valid blood sample for immunogenicity analysis after Sirukumab dose. This analysis set will be used to analyze immunogenicity using the actual treatment received by a participant (IMG analysis set as Treated).

2.2.7 Per-Protocol (PP) Analysis Set

The PP analysis set consists of participants in ITT analysis set who don't have any major protocol deviations that could have influenced the efficacy of Sirukumab during the study. This analysis set will be used for exploratory analysis of primary efficacy endpoint if more than 10% of ITT participants have major protocol deviations that could have influenced the efficacy evaluation.

2.3 Study Day 1

Study Day 1 refers to the day/date of the study drug administration (which is the same as the treatment phase start date).

2.4 Imputation of Missing Time Portion of Date/Time Field

Each measurement/observation which is supposed to have date and time associated with it may sometimes have the time portion of date/time as missing. If time is missing, then the measurement/observation is assumed to be at the start of the day (that is, missing time is imputed as 00:00:00 hours/minutes/seconds). Therefore, a measurement/observation with missing time on Day 1 is assumed to be pre-dose unless information on eCRF clearly mentions that it is post-dose.

2.5 Baseline Value

The baseline values for efficacy endpoints are defined in section 5: Efficacy.

For demographics and other measurements during the study, a baseline is defined as the last value/measurement (1) on or after informed consent date/time, AND (2) before the date/time of study drug administration.

However, following exceptions apply to define the baseline.

- (1) For electrocardiogram (ECG) measurements, for participants who were enrolled before protocol amendment 5, the baseline is defined as the last value/measurement (1) on or after

informed consent date/time, AND (2) before the date/time of study drug administration. For participants who were enrolled based on protocol amendment 5, the baseline may be defined using information from up to 2 days prior to the informed consent date.

- (2) Local labs tests (blood chemistry, hematology, coagulation tests), pregnancy tests and chest imaging, the baseline may be defined using the information from up to 2 days prior to the informed consent date.
- (3) It is possible that for some biomarkers there are multiple samples taken at the same date/time providing different test results corresponding to the same date/time. In such cases when there are multiple pre-dose measurements exactly on the same date/time that are closest to date/time of study drug administration then average of these measurements is used as baseline value. [Note: Measurements below lower limits of quantification (LLOQ) will be imputed by LLOQ/2 and measurements above upper limits of quantification (ULOQ) by ULOQ prior to taking the average, if required.]
- (4) The baseline for viral load may be a post-dose measurement, for more details please see section 6.2: Virology Assessments- Definitions.
- (5) If pre-dose height and weight values are not available, then earliest post-dose values on day of study drug administration may be used as the baseline values for height and weight.

[Note: As mentioned in section 2.4, a measurement/observation with missing time on Day 1 is assumed to be pre-dose unless information on eCRF clearly mentions that it is post-dose.]

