Self-reported oxygen needed (yes/no)					X ⁿ	X ⁿ		
Self-reported pregnancy status					X ⁿ	X ⁿ		
Record readmission(s) post discharge and reason					X ⁿ	X ⁿ		

- Laboratory testing to be performed centrally

Note: If multiple assessments are scheduled for the same timepoint, it is recommended that procedures be performed in the following sequence: ECG, oxygen saturation, vital signs, blood sampling.

Abbreviations: AE: adverse event, AESI: adverse event of special interest; aPPT: activated partial thromboplastin time; CRP: C-reactive protein; CT: computed tomography; DBP: diastolic blood pressure; FiO₂: percentage of inspired oxygen; ECG: electrocardiogram; HDL: low-density lipoprotein; ICF: informed consent form; ICU: intensive care unit; INR: international normalized ratio; LDL: low-density lipoprotein; PaCO₂: partial pressure of carbon dioxide in arterial blood; PaO₂: partial pressures of oxygen in arterial blood; PCR: polymerase chain reaction; PT: prothrombin time; SAE: serious adverse event; SBP: systolic blood pressure; SOC: standard of care; SpO₂: peripheral capillary oxygen saturation.

Footnotes:

- a. Screening assessments start after signing of the ICF and can continue on the next calendar day, if needed. All screening and baseline assessments may also take place on the same day. Screening/Baseline assessments required to verify study eligibility and data collection for assessment of the 6-point ordinal clinical recovery category should take place prior to randomization. All Screening/Baseline procedures should take place prior to study drug administration.
- b. The assessment schedule will be on a weekly basis for participants still hospitalized after Day 28. For the required assessments, refer to Section [10.3, Appendix 3: Clinical and Laboratory Assessments Described per Day](#).
- c. Consent to be obtained before the first study-related activity. An exception is in the case of an emergency enrollment in which the informed consent can be obtained as soon as possible.
- d. If a participant's clinical status changes after screening but before randomization such that he or she no longer meets all eligibility criteria, then the participant should be excluded from participation in the study.
- e. Medical history should include collecting onset of COVID-19 symptoms, prior therapy, and date of SARS-CoV-2 diagnosis if available.
- f. A urine pregnancy test is to be performed in women of childbearing potential only.

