4.2.1. Study-Specific Ethical Design Considerations

Potential participants or (legally acceptable representatives) will be fully informed of the risks and requirements of the study and, during the study, participants (or legally acceptable representatives) will be given any new information that may affect their decision to continue participation. They will be told that their consent to participate in the study is voluntary and may be withdrawn at any time with no reason given and without penalty or loss of benefits to which they would otherwise be entitled. Participants (or legally acceptable representatives) who are fully able to understand the risks, benefits, and potential AEs of the study, and provide their consent voluntarily will be enrolled.

In case of emergency situations due to COVID-19, when patients are incapable of giving their informed consent (eg, under intensive medical care) to enter the study, and the participant's legally acceptable representative is not available (eg, none is in place since the participant had been otherwise healthy before infection with SARS-CoV-2), deferred consent is permitted if in compliance with national law and local regulations. Enrollment procedures should be described in the protocol with documented approval/favorable opinion by the IEC/IRB to protect the rights, safety, and well-being of the participant and to ensure compliance with applicable regulatory requirements. The participant or legally acceptable representative should be informed about the study as soon as possible and give consent to continue. In the event the legally acceptable representative is not available, a member of the family can take that role.

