8.3. Adverse Events, Serious Adverse Events, and Other Safety Reporting

Timely, accurate, and complete reporting and analysis of safety information, including AEs, SAEs, and product quality complaints (PQCs), from clinical studies are crucial for the protection of participants, investigators, and the sponsor, and are mandated by regulatory agencies worldwide. The sponsor has established Standard Operating Procedures in conformity with regulatory requirements worldwide to ensure appropriate reporting of safety information; all clinical studies conducted by the sponsor or its affiliates will be conducted in accordance with those procedures.

Adverse events will be reported as specified in Section 8.3.1 by the participant (or, when appropriate, by a caregiver, surrogate, or the participant's legally acceptable representative) for the duration of the study.

Further details on AEs, SAEs, and PQCs can be found in Section [10.5, Appendix 5](#) Adverse Events, Serious Adverse Events, Product Quality Complaints, and Other Safety Reporting: Definitions and Procedures for Recording, Evaluating, Follow-Up, and Reporting.

8.3.1. Time Period and Frequency for Collecting Adverse Event and Serious Adverse Event Information

All Adverse Events

All adverse events and special reporting situations, whether serious or non-serious, will be reported from the time a signed and dated ICF is obtained until completion of the participant's last study-related procedure, which may include phone call contact for follow-up of safety.

Serious Adverse Events

All SAEs, as well as PQCs, occurring during the study must be reported to the appropriate sponsor contact person by study-site personnel within 24 hours of their knowledge of the event.

Serious adverse events, including those spontaneously reported to the investigator through the Week 16 phone call visit, must be reported using a Serious Adverse Event form. The sponsor will evaluate any safety information that is spontaneously reported by an investigator beyond the time frame specified in the protocol.

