10.4.3. Informed Consent Process

Consent of each participant (or legally acceptable representative based on local regulations) must be obtained according to local requirements after the nature of the study has been fully explained. The informed consent (s) must be obtained before performance of any study-related activity. The ICF(s) that is/are used must be approved by both the sponsor and by the reviewing IEC/IRB and be in a language that the participant can read and understand. The informed consent should be in accordance with principles that originated in the Declaration of Helsinki, current ICH and GCP guidelines, applicable regulatory requirements, and sponsor policy.

Before enrollment in the study, the investigator or an authorized member of the study-site personnel must explain to potential participants or their legally acceptable representative (based on local regulations) the aims, methods, reasonably anticipated benefits, and potential hazards of the study, and any discomfort participation in the study may entail. They will be informed that participation is voluntary and that they may withdraw consent to participate at any time. They will be informed that choosing not to participate will not affect the care the participant will receive for the treatment of his or her disease. Finally, they will be told that the investigator will maintain a participant identification register for the purposes of long-term follow up if needed and that their records may be accessed by health authorities and authorized sponsor personnel without violating the confidentiality of the participant, to the extent permitted by the applicable law(s) or regulations.

For more information on emergency situations due to COVID-19, see also Section [4.2.1](#).

By obtaining the informed consent the participant or legally acceptable representative (based on local regulations) is authorizing such access, which includes permission to obtain information about his or her survival status. It also denotes that the participant agrees to allow his or her study physician to recontact the participant for the purpose of obtaining consent for additional safety evaluations, and subsequent disease-related treatments, if needed.

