2.1.1 Phase Definitions

Table 1: Construction of phases

| Study Phase | Start Date/Time | End Date/Time |
|---------------------|---|--|
| Screening (phase 1) | The date & time of signing the informed consent ^{*1} | 1 minute before the study drug intake |
| Treatment (phase 2) | Date & time of study drug administration (Sirukumab or Placebo) ^{*2} | Minimum of: a. Day 28 Visit at 23.59h or if Discharged earlier phone call Day 28 at 23.59h b. Date of study discontinuation before Day 28 ^{*3} c. Date of death ^{*3} If a), b) c) did not occur then count 28 days after drug administration at 23.59h |
| Follow-up (phase 3) | End of the treatment phase +1 minute | Maximum of: a. Date of last contact ^{*3} b. Date of study discontinuation ^{*3} |

^{*1}: if no time is available then impute with 00:00

^{*2}: in case the time part of the study drug administration is missing then time part will be imputed by time of randomization

^{*3}: Time will be imputed with 23:59

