9.2.2 Data Handling Rules

For lab tests from local labs the local lab reference ranges will be used to determine the lab abnormalities.

Imputations of numerical values expressed as characters

In case a laboratory test result is censored (no numeric value is available, but only a verbatim term), the following rules are applied:

- ‘ $<x$ ’ or ‘ $>x$ ’: a numeric value will be imputed by the cut-off value decreased or increased with one unit respectively

- ‘ $\leq x$ ’ or ‘ $\geq x$ ’: imputation by x.

Toxicity grades and abnormalities for laboratory parameters

The laboratory toxicity will be determined according to the criteria specified in the adult toxicity grading table by ‘Division of Microbiology and Infectious Diseases’ (DMID). In case no toxicity grades are defined for a test, the abnormalities (above/below normal range) will be used.

In determining toxicity grades/abnormalities for each subject the following rules are applied:

- Baseline toxicity grade/abnormality will be based on the baseline value (see section 4.1 for the baseline definition).
- Worst grades/abnormalities during treatment phase are determined over the treatment phase, including all scheduled and unscheduled measurements of that phase.
- The abnormalities “abnormally low” and “abnormally high” are considered equally important, i.e. if a subject has an abnormally low as well as an abnormally high value post-baseline, both abnormalities will be shown in the tables. (This implies that the sum of the percentages can be more than 100%).
- If, for a specific test, the grading list provides distinct limits for abnormally low (=hypo) values as well as for abnormally high (=hyper) values, this test should be repeated for hyper and hypo limits separately in cross-tabulations.

Treatment-emergent definition for toxicity grades and abnormalities

A toxicity grade/abnormality will be considered treatment-emergent if it is worse than the baseline grade/abnormality. If the baseline grade/abnormality is missing, the abnormality is always considered as treatment-emergent. A shift from “abnormally low” at baseline to “abnormally high” post-baseline (or vice versa) is also treatment-emergent.

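### If consent is signed after dosing, as the deferred-consent route allows, the SAP baseline window is empty for vital signs, pre-Amendment 5 ECGs and central-lab biomarkers, and adverse event collection starts late

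*SAP*

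**What the plan says.** **Consent.** Protocol 10.4.3 states the general rule that consent "must be obtained before performance of any study-related activity". Protocol 4.2.1 makes an exception for an emergency in which the patient cannot consent and no legally acceptable representative is available: "deferred consent is permitted if in compliance with national law and local regulations". It then adds: "The participant or legally acceptable representative should be informed about the study as soon as possible and give consent to continue". Footnote c of the Schedule of Activities (Protocol 1.3) agrees: "An exception is in the case of an emergency enrollment in which the informed consent can be obtained as soon as possible".

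**Baseline.** The general rule in SAP 2.5 is that "baseline is defined as the last value/measurement (1) on or after informed consent date/time, AND (2) before the date/time of study drug administration". Among its exceptions:
- Local laboratory tests, pregnancy tests and chest imaging may use data from up to 2 days before the consent date.
- ECGs have the same look-back, but only for participants enrolled under Amendment 5. The consent condition is restated for earlier enrollees.
- Height and weight may fall back on a post-dose value from the dosing day.

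**Phases.** In SAP Table 1 (section 2.1.1) screening starts at "The date & time of signing the informed consent" and ends one minute before dosing.

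**Missing baseline.** For laboratory tests, SAP 9.2.2 says: "If the baseline grade/abnormality is missing, the abnormality is always considered as treatment-emergent". SAP 9.3.2 (vital signs) and 9.4.2 (ECG) apply the same rule.

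**Adverse events.** Protocol 8.3.1 says that adverse events "will be reported from the time a signed and dated ICF is obtained". SAP 9.1.1 uses the same starting point.

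**The concern.** Three analysis rules (baseline, start of screening, start of adverse event collection) assume that consent comes before dosing. The protocol provides a route on which it need not. The deferred consent is consent to continue, and Protocol 6.1 requires dosing no later than 6 hours after randomization, so a signature after the infusion is a foreseeable result. The SAP has no rule for that case.

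The stake is the safety tabulations. A participant who had tachycardia or fever before the infusion would be listed with a treatment-emergent abnormality, because the pre-dose measurement exists but is not admissible. The visit-to-baseline biomarker ratios in SAP 7.3.1 could not be formed for that participant. A non-serious reaction in the hours after a single infusion could fall before the stated start of collection, although hypersensitivity is an event of special interest and Protocol 9.4.6 counts events as treatment-emergent from dosing onward.

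**Working it through.** The plan gives no figure on this point to reproduce. The check applies the date rules.

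**Inputs.** Let D be the time of dosing and C the time of consent.
- General window (SAP 2.5): from C up to, but not including, D.
- Look-back window (SAP 2.5 exceptions): from the consent date minus 2 days up to D.
- Screening length (SAP Table 1): (D − 1 minute) − C.
- For illustration, D is 14:00 on Day 1, with values measured 48, 30 and 2 hours before dosing.

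**Step 1: baseline and screening phase.** The general window contains a time point only if C is before D.

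| Consent relative to dosing | General rule | 2-day look-back | Screening length |
|---|---|---|---|
| 6 h before | 2 h pre-dose value | 2 h pre-dose value | +5.98 h |
| 0.5 h after | none | 2 h pre-dose value | −0.52 h |
| 24 h after | none | 2 h pre-dose value | −24.02 h |
| 57.9 h after | none | 2 h pre-dose value | −57.92 h |
| 58.1 h after | none | none | −58.12 h |
| 168 h after | none | none | −168.02 h |

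The look-back fails between 57.9 and 58.1 hours because consent then passes midnight into Day 4, and Day 4 minus 2 days is Day 2, which is after dosing.

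**Step 2: which measurements depend on which rule.**

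| Measurement | Consent after dosing |
|---|---|
| Vital signs | baseline lost (no exception) |
| ECG, enrolled before Amendment 5 | baseline lost |
| Central-lab biomarkers | baseline lost (exception covers local labs only) |
| Local labs; ECG under Amendment 5 | lost only if the consent date is more than 2 days after the last pre-dose value |
| Height, weight | same-day post-dose fallback |
| Clinical recovery scale (SAP 5.2.1) | unaffected: tied to the randomization request |
| Viral load (SAP 6.2) | unaffected: last pre-dose value, no consent condition |

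**Step 3: consequence.** For the first two rows, SAP 9.3.2 and 9.4.2 turn a missing baseline into an automatic treatment-emergent label for any post-dose abnormality.

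**Step 4: adverse events.** SAP 9.1.2 assigns events to phases by onset relative to dosing, so a recorded pre-dose event still goes to screening and a recorded post-dose event to treatment. The gap lies in collection: Protocol 8.3.1 and SAP 9.1.1 start it at the signed form. For serious events, another sentence of Protocol 8.3.1 requires reporting of all those occurring during the study, with no consent condition, so their coverage is ambiguous.

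**Step 5: scale (assumptions only).** The documents give no count of deferred consents. Let s be the share of the 111 critical participants dosed before consent, and p the share of those with a pre-existing abnormality on a given vital sign that persists after dosing. Wrongly labelled participants are then up to 100 × s × p percentage points.

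| s | of 111 | p = 30% | p = 60% | p = 90% |
|---|---|---|---|---|
| 1% | 1.1 | 0.3 | 0.6 | 0.9 |
| 5% | 5.6 | 1.5 | 3.0 | 4.5 |
| 10% | 11.1 | 3.0 | 6.0 | 9.0 |
| 20% | 22.2 | 6.0 | 12.0 | 18.0 |

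With the planned 74 and 37 per arm, one mislabelled participant moves the percentage by 1/74 = 1.4 points on sirukumab or 1/37 = 2.7 points on placebo.

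**The case against.** The best reply is that the trigger is narrow. Deferred consent needs an emergency, an incapable patient, no available representative and permissive law. A family member may stand in for the representative, and telephone consent is provided for. Footnote c says as soon as possible, not after dosing, and up to 6 hours may pass between randomization and infusion. Both arms follow the same rule, adverse events are not formally tested, and treatment-emergent is not the same as related. All of this stands. It limits the size of the problem, but it does not supply a rule for the case the protocol permits.

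A reader might also infer more than the documents support:
- **That all baselines are lost.** The look-backs, the height and weight fallback, and the separate rules for the recovery scale and viral load prevent this.
- **That every pre-existing abnormality becomes treatment-emergent, including lymphopenia or raised ALT.** Those are local laboratory tests and keep their baseline unless the consent date is more than 2 days after the sample. Recorded pre-dose adverse events stay in screening.
- **That events between dosing and consent are all unreported.** For serious events the text is ambiguous. The Schedule of Activities also lists adverse events at screening, at baseline and throughout the study.
- **That the covariate-adjusted efficacy models lose IL-6, CRP and ferritin.** SAP 5.2.3 and 5.3.3 name screening values, and the SAP does not say that the rule in 2.5 governs them. These are sensitivity analyses in any case.

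**Conclusion.** The concern holds in a limited form. When consent is signed after dosing, the stated rules give wrong results: no admissible baseline for vital signs, pre-Amendment 5 ECGs and central-lab biomarkers; an automatic treatment-emergent label for any post-dose vital-sign abnormality, or ECG abnormality in those earlier enrollees; no biomarker ratios; a screening phase of negative length; and, read literally, a late start of non-serious adverse event collection. Local laboratory tests and Amendment 5 ECGs join the list only when the consent date is more than 2 days after the last pre-dose value.

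The expected effect is inflated incidence in both arms rather than a bias for or against sirukumab. The endpoints based on the recovery scale, the power and the alpha are not affected. The number of such participants is not given and may be zero; the ranges above rest on assumed shares. The point deserves correction because the rule is wrong as written and the repair is small, not because it threatens the main conclusions.

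**What to change.** - **SAP 2.5:** define baseline as the last value before study drug administration regardless of the consent date, where use of the data is permitted. Keep the 2-day look-back, but count it from the start of screening. The SAP already anchors the viral-load baseline to dosing in section 6.2.
- **SAP Table 1:** start the screening phase at the earlier of consent and the first screening procedure.
- **Protocol 8.3.1 and SAP 9.1.1:** collect adverse events from the earlier of consent and study drug administration, once consent to continue and to use the data has been obtained.

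The cost is a few sentences in the two documents and a change to the baseline and phase derivations before database lock. No new data are needed beyond events already charted. Reporting how many participants signed consent after dosing would show whether the case arose at all.
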